1) the use of research drugs is not consistent with the clinical regimen, and has a significant impact on the evaluation of efficacy and safety, 2) those without any record, 3) those who did not take research drugs.

TACE Failure Criteria:

1) Intrahepatic lesion [i, two or more consecutive ineffective responses seen within the treated tumors (viable lesion >50%), even after changing the chemotherapeutic agents and/or reanalysis of the feeding artery, on response evaluation CT/MRI after 1–3 months following adequately performed selective TACE. ii, two or more consecutive progressions in the liver (including an increase in the number of tumors compared to that before the previous TACE procedure), even after changing the chemotherapeutic agents and/or reanalysis of the feeding artery, on response evaluation CT/MRI after 1–3 months following adequately performed selective TACE]. 2) Continuous elevation of tumor markers right after TACE, even though transient minor reduction is observed. 3) Appearance of vascular invasion. 4) Appearance of extrahepatic spread.

4. Endpoints and Definitions

The primary endpoint is the PFS, i.e., the time from enrollment to disease progression according to the modified RECIST (mRECIST) guideline in trial immunotherapeutics, or death from any cause, whichever occurred first. Secondary endpoints include overall survival (OS), objective response rate (ORR), disease control rate (DCR), quality of life (QoL), and safety. Patients without any post-baseline tumor assessment are considered non-responders. Objective responses

will be confirmed at least 28 days after the initial documentation of the response.

Progression-Free Survival: Time from the date of enrollment to the date of first documentation of tumor progression.

Progression was defined using Modified RECIST (mRECIST): an increase of at least 20% in the sum of the diameters of viable (enhancing) target lesions, taking as reference the smallest sum of the diameters of viable (enhancing) target lesions recorded since treatment started.

Overall survival: time from the date of enrollment to the date of death from any cause.

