The trial was designed to use a 2-sided 5% type I error and had 80% power to detect an improvement in PFS from 1.5 months in the TAE group to 4.5 months in the TAE-iNKT group, corresponding to a hazard ratio (HR) of 0.33 in terms of median PFS. In consideration of these assumptions, the trial design was powered for 60 patients to be randomly assigned in each group as the intention-to-treat population (allocation ratio of 1:1, n=30 patients in each group), and allowing for a drop-out rate of 20%. Sample size estimation was performed using PASS 11.

Continuous variables will be expressed as the median and IQR, and will be compared using t tests or Mann-Whitney tests. Categorical variables will be presented as the frequency and percentage, and will be compared using Fisher's exact tests. Survival and time to QoL deterioration will be estimated using the Kaplan-Meier method, and their 95% CIs will be calculated using the Brookmeyer and Crowley method. Survival differences will be compared using log-rank tests. Peripheral blood cells will be analyzed using Sidak's multiple comparison test. The overall two-sided significance level of $P < .05$ will be split into a two-sided significance level of $P < .01$ for tests of PFS, OS, ORR, DCR, and QoL according to the Bonferroni method (dividing the available total α (typically 0.05) equally among the chosen endpoints). If the PFS and/or all secondary endpoints are statistically significant at a two-sided significance level of 0.01, the curative effect of TAE-iNKT will be deemed better than that of TAE alone. All statistical analyses will be conducted using SAS software version 9.4 (SAS Institute).

8. Data Management.

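### The sample-size sentence gives both 60 and 30 patients in each group, and no PFS power is stated at the two-sided 1% level that decides PFS

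*Combined protocol and SAP*

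**What the plan says.** Section 4 (Endpoints and Definitions) names the primary endpoint: "The primary endpoint is the PFS".

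Section 7 (Statistical Analysis) opens with the power statement: "The trial was designed to use a 2-sided 5% type I error and had 80% power". The effect to be detected is a rise in median PFS from 1.5 to 4.5 months, given as a hazard ratio of 0.33. The next sentence says "the trial design was powered for 60 patients to be randomly assigned in each group as the intention-to-treat population", adds in parentheses a 1:1 allocation and "n=30 patients in each group", and closes with "allowing for a drop-out rate of 20" per cent. The tool is named, "Sample size estimation was performed using PASS 11", but the PASS procedure, the expected number of events, the accrual period, the follow-up and the handling of drop-outs are not given.

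The following paragraph divides the overall two-sided 5% into 1% "for tests of PFS, OS, ORR, DCR, and QoL according to the Bonferroni method". The rule for declaring benefit begins: "If the PFS and/or all secondary endpoints are statistically significant at a two-sided significance level of 0.01".

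Section 2 gives the only time frame, March 2018 to March 2020, and does not separate accrual from follow-up. Section 6 repeats the 1:1 randomisation without a number.

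**The concern.** The two halves of one sentence differ by a factor of two. A site, an ethics committee or a later reader cannot tell from the text whether 60 randomised patients complete the trial or are half of it.

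The power statement has a separate problem. Power belongs to a particular test at a particular level. The plan attaches 80% to a two-sided 5% error rate, but PFS counts as positive only at two-sided 1%. The stricter level needs about half as many events again (38.71/26.01 = 1.49), so a power quoted at 5% says little about the test that will be run. The plan does not say at which level the trial was sized.

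**Working it through.** **Inputs from the plan.** Medians 1.5 and 4.5 months, so HR = 1.5/4.5 = 0.333; power 80%; two-sided 5% (power statement) or 1% (PFS test); drop-out 20%; 1:1 allocation; log-rank test (all Section 7).

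**Step 1: the two sample sizes.** 60 in each of two groups is 120; 30 in each is 60. Nothing else in the documents settles which is meant.

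**Step 2: events for 80% power.** z for power = 0.842; z for two-sided 5% = 1.960 and for 1% = 2.576. The squared sums are 7.849 and 11.679, and ln(0.333)² = 1.207.

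- Schoenfeld, 4(z_a + z_b)²/ln(HR)²: 4 × 7.849/1.207 = 26.01 at 5%; 4 × 11.679/1.207 = 38.71 at 1%.
- Freedman, (z_a + z_b)² × [(1 + HR)/(1 − HR)]², where the bracket is 2 and its square 4: 4 × 7.849 = 31.40 at 5%; 4 × 11.679 = 46.72 at 1%.

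**Step 3: patients in total**, if every retained patient has an event (events rounded up, divided by 0.8, rounded up again):

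| Level | Schoenfeld | Freedman |
|---|---|---|
| Two-sided 5% | 27/0.8 → 34 | 32/0.8 = 40 |
| Two-sided 1% | 39/0.8 → 49 | 47/0.8 → 59 |

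The plan's figure is therefore not reproduced at 5% in this simplest case. A total of 60 is reproduced at 1% with Freedman. It is also reached at 5% if follow-up is short: with exponential PFS, a fixed 3 months per patient gives 58 (Schoenfeld) and a fixed 4 months gives 60 (Freedman). The plan states no such follow-up.

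**Step 4: power at two-sided 1% with 60 randomised and 48 retained (60 × 0.8).** Assumptions not in the documents: exponential PFS, uniform accrual over A months, at least F months of follow-up, data cut-off at the end of the 24-month window, and drop-outs contributing nothing. The event probability in each group is 1 − [exp(−lF) − exp(−l(A + F))]/(lA), with l = ln 2/median. Power is Φ(√d × |ln HR|/2 − 2.576) by Schoenfeld and Φ(√d × (1 − HR)/(1 + HR) − 2.576) by Freedman, where d is the number of events.

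| A + F (months) | Event probability, TAE / TAE-iNKT | Events among 48 | Freedman | Schoenfeld | Simulated log-rank |
|---|---|---|---|---|---|
| All have events | 1 / 1 | 48 | 81.3% | 89.1% | 83.8% |
| 12 + 12 | 0.999 / 0.928 | 46.3 | 79.5% | 87.7% | 83.7% |
| 20.3 + 3.7 | 0.981 / 0.827 | 43.4 | 76.3% | 85.1% | 81.5% |
| 24 + 0 | 0.910 / 0.736 | 39.5 | 71.5% | 81.0% | 76.4% |

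The simulations of the three accrual patterns used 100,000 trials each (Monte Carlo error about 0.1 points).

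If drop-outs lose no information, so that all 60 count, the 1% formula range is 82.6% (24 + 0, Freedman) to 95.3% (all have events, Schoenfeld). If 120 are randomised and 96 retained, it is about 97% or more across the same accrual patterns.

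**The case against.** The strongest reply is that one reading reconciles the section: 60 in total, 30 per group, with 5% as the trial-wide level that the Bonferroni paragraph divides. On that reading the Freedman figure at 1% is 59, in effect 60, and the wording is merely loose. Much of this stands. A trial-wide 5% with PFS at 1% is coherent, and 60 in total is the likelier reading. But both points are inferences, and the first still leaves the plan without a stated power at 1%.

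The reply also limits what can be concluded. A reader might infer three stronger things, none of which the documents support:

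- *The PFS test is underpowered at 1%.* The result falls on either side of 80% according to accrual, follow-up and drop-out handling that the plan does not give.
- *The stated size is an arithmetic error.* The PASS settings are not reported, short follow-up at 5% also gives about 60, and exceeding a minimum size is not an error.
- *120 can be ruled out by calculation.* It cannot: at 1%, Freedman with a fixed 2.4 months of follow-up gives about 119. The preference for 60 rests on the wording and on the simplest calculation.

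Nor does the imaging schedule in Section 6 fix a minimum follow-up. Week 16 is where scans change from every 4 to every 8 weeks, continuing until radiological progression. The 3.7-month (16-week) row above is therefore only an illustration.

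**Conclusion.** Two defects stand on the page and need no modelling. The planned sample size is contradictory by a factor of two, and the only power figure for the primary endpoint is given with a level other than the one at which that endpoint is tested.

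The calculation adds that a total of 60 fits sizing at 1%, or sizing at 5% with short follow-up that is not stated; the documents do not show which was done. If 60 is the total, formula power at 1% runs from about 71% to 89% with 48 retained, and up to about 95% with no loss of information. This rests on the plan's hazard ratio and on the assumed exponential PFS, accrual, cut-off and drop-out handling. No definite shortfall is claimed. If 120 is the total, power at 1% is ample under the accrual patterns tried, and only the contradiction and the missing power statement remain. The correction is necessary because readers rely on these figures to judge the size of the trial and its primary test.

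**What to change.** Replace the sample-size sentences in Section 7 with one paragraph, figures to be supplied by the sponsor:

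*A total of [N] patients ([N/2] in each group) will be randomised 1:1. With [D] expected PFS events, from [A] months of accrual, [F] months of minimum follow-up and 20% drop-out handled as [rule], a log-rank test at two-sided 1% has [x]% power to detect a hazard ratio of 0.33 (PASS 11, [procedure]).*

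The sponsor must confirm which number was planned. If sizing was done at 1%, correct the two-sided 5% phrase or label it as the overall level before the split. If it was done at 5%, say so and give the power at 1% beside it.

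The cost is one paragraph, with no change to the endpoint or the test. The downside is that the restated power may differ from 80% and could be several points lower; whether to act on that is for the sponsor to decide.

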Objective response rate: including complete response (CR) and partial response (PR) evaluated by imaging according to mRECIST for target lesions and assessed by MRI/CT. Complete Response (CR), disappearance of any intratumoral arterial enhancement in all target lesions. Partial Response (PR), at least a 30% decrease in the sum of diameters of viable (enhancement in the arterial phase) target lesions, taking as reference the baseline sum of the diameters of target lesions. Objective Response Rate = CR + PR.

Disease Control Rate: including complete response (CR), partial response (PR), and disease stabilization (SD), evaluated by imaging according to mRECIST for target lesions and assessed by MRI/CT. Complete Response (CR), disappearance of any intratumoral arterial enhancement in all target lesions. Partial Response (PR), at least a 30% decrease in the sum of diameters of viable (enhancement in the arterial phase) target lesions, taking as reference the baseline sum of the diameters of target

lesions. Stable disease (SD), any cases that do not qualify for either partial response or progressive disease. Disease Control Rate = CR + PR + SD.

The Quality of Life (QoL) will be assessed according to the EORTC (EORTC: the European Organization for Research and Treatment of Cancer) QLQ-C30 scale between the TAE-iNKT and TAE group. And the time to deterioration of QoL, as reported by the patient, with deterioration defined as a decrease from baseline of 10 points or more on the EORTC QLQ-C30 maintained for two consecutive assessments.

Safety and side-effect profiles will be assessed based on the nature, frequency, and severity of adverse events, according to the National Cancer Institute (NCI) Common Terminology Criteria for Adverse Events (CTCAE), version 4.0.3. Common Adverse events (AEs) occurring on or after the first treatment day through the end of this trial will be recorded according to NCI-CTCAE 4.03.

5. Drugs for research

Name of Drug

iNKT cells

Production of iNKT Cells

- 1) Isolate PBMCs by leukapheresis using a COM.TEC apheresis system and Lymphoprep density gradient medium.
- 2) Resuspend PBMCs in Corning serum-free cell medium KBM581 and stimulate with 100 ng/mL α -GalCer and 100 U/mL animal-free recombinant human

interleukin-2 for 48 hours; the rhIL-2 was replenished every other day.

3) Stimulate PBMCs with 1,000 IU/mL granulocyte-macrophage colony-stimulating factor and IL-4 for 1 week, and obtain mature, monocyte-derived DCs.

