radiological progression. At the same time points, routine blood tests, tumor biomarkers, α -fetoprotein (AFP), and quality of life (QoL) will be measured.

After the end of treatment, the survival follow-up of the subjects will continue to be conducted every 3 months, while those who end treatment for reasons other than disease progression will undergo regular tumor imaging evaluation as much as possible after treatment, and survival follow-up must be carried out.

The details of follow-up are shown in the table below:

Project / time	Screening/ baseline period (-14d~0w)	The first cycle 3W \pm 7d	The second cycle 6w \pm 7d	Odd cycle \pm 7d	Even cycle \pm 7d	Out-of- group follow-up \pm 7d
Sign the informed consent form	×					
Medical history	×					
Inclusion / exclusion criteria	×					
Physical examination and vital signs	×	×	×	×	×	×
Blood routine	×	×	×	×	×	×
Urine routine	×	×	×	×	×	×
Biochemistry (liver and kidney function, blood glucose, blood lipid)	×	×	×	×	×	×
Myocardial enzyme	×	×	×	×	×	×
Thyroid function	×	×	×	×	×	×
Five items of hepatitis B	×					
Hepatitis C antibody	×					
HBV-DNA/HCV RNA quantification	×		×		×	×
Syphilis antibody	×					
HIV antibody	×					
Digestive tumor markers, AFP	×	×	×	×	×	×
Coagulation	×	×	×	×	×	×

Autoantibody	×					
T cell subsets	×	×	×	×	×	×
Detection of cell suspension (bacteria, fungi, endotoxin)	×	×	×	×	×	
Electrocardiogram	×		×		×	×
Colour Sonography	×					×
Liver enhanced MR or CT	×		×		×	×
Imaging data of other organs	×		×		×	×
Pathological examination of tumor	×					
Drug combination	×	×	×	×	×	×
Adverse events	×	×	×	×	×	×

The Implementation of TAE

- 1) Select catheterization of the feeding artery by using a microcatheter.
- 2) Perform abdominal and hepatic arteriography.
- 3) Embolization with Gelfoam until near stasis of the arterial flow.
- 4) Determine the dose of iodized oil by the tumor size or based on whether the portal vein had a tumor thrombosis.
- 5) Inject the emulsion of iodized oil until the accumulation of the emulsion in the tumor and the visualization of the portal vein branches near the tumor. (If there was a significant arteriportal shunt, embolization with Gelfoam was first performed to occlude the shunt, after which the iodized oil emulsion was infused, and embolization with Gelfoam was performed.)

7. Statistical Analysis

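### The only test Section 7 offers for QLQ-C30 scores is an unadjusted t or Mann-Whitney test; a baseline-adjusted repeated-measures analysis with one named contrast would use the data better

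*Combined protocol and SAP*

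**What the plan says.** Section 4 (Endpoints and Definitions) lists QoL as a secondary endpoint and describes two measures. The first is a comparison on the "QLQ-C30 scale between the TAE-iNKT and TAE group". The second is time to deterioration, defined as a fall of at least 10 points from baseline that persists over two consecutive assessments.

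Section 6 (Interventions) sets imaging at baseline, every 4 weeks to week 16, then every 8 weeks until radiological progression. At those same time points "quality of life (QoL) will be measured". The follow-up table in Section 6 has no QoL row, so this sentence is the only source for the QoL schedule.

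Section 7 (Statistical Analysis) assigns Kaplan-Meier estimation to time to deterioration. For the scores, the only rule that can apply is the general one: "Continuous variables will be expressed as the median and IQR, and will be compared using t tests or Mann-Whitney tests". Section 7 also gives QoL a two-sided 0.01 test, as one of five endpoints sharing 0.05, and counts all secondary endpoints in its success rule. It does not say which of the two QoL measures takes that test.

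**The concern.** The score is a repeated measure with a baseline value. A two-sample test at one visit uses neither the baseline nor the other visits. With 30 patients per arm and a 0.01 threshold, chance imbalance at baseline passes straight into the comparison, and available precision is lost.

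Because QoL forms follow imaging visits that end at radiological progression, patients who progress early drop out of later comparisons. If TAE-iNKT delays progression as the design assumes, this happens faster in the TAE arm. A late cross-sectional test then compares a small, better-faring part of one arm with a larger part of the other, which is no longer the randomised comparison.

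The plan also leaves open the QLQ-C30 scale, the visit, and the criterion for choosing between the t and Mann-Whitney tests. In an open-label trial, an endpoint that may carry alpha should have these fixed in advance.

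**Working it through.** **Inputs from the documents (Section 7).** Median PFS 1.5 and 4.5 months ("an improvement in PFS from 1.5 months in the TAE group to 4.5 months in the TAE-iNKT group"); "allocation ratio of 1:1, n=30 patients in each group"; two-sided 0.01 for QoL. Visit weeks are from Section 6.

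**Inputs assumed.** The documents give no SD, QoL effect or baseline-to-visit correlation *r*. I take a difference of d = 0.67 SD and r = 0.3, 0.5 and 0.7, with exponential PFS and no other drop-out.

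**The plan's own figures.**
- Hazard ratio: 1.5/4.5 = 0.33, as stated.
- Alpha share: 0.05/5 = 0.01, as stated.
- Sample size: this is calculated for PFS only. Freedman's formula at two-sided 0.01 gives (2.576 + 0.842)² × (1.333/0.667)² ≈ 47 events, and 47/0.8 ≈ 59 patients, close to 60. The sample-size sentence itself states 5%, which is a separate matter. No size or power is given for QoL.

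**Step 1: gain from baseline adjustment.** The variance of a baseline-adjusted comparison at one visit is (1 − r²) times the unadjusted variance. The reduction r² is 9%, 25% and 49% at r = 0.3, 0.5 and 0.7.

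**Step 2: who is due a form at each visit.** With 4.348 weeks per month, the medians are 6.52 and 19.57 weeks. The expected number progression-free at week w is 30 × exp(−ln 2 × w/median). A patient whose progression is found at a given scan is still scheduled for that visit's form, so those due at a visit are those not yet progressed at the previous one.

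| Visit | Not progressed at | TAE due | TAE-iNKT due |
|---|---|---|---|
| Week 4 | Baseline | 30 | 30 |
| Week 8 | Week 4 | 19.6 | 26.0 |
| Week 12 | Week 8 | 12.8 | 22.6 |
| Week 16 | Week 12 | 8.4 | 19.6 |

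**Step 3: power.** Power = Φ( d / √[(1 − r²)(1/n₁ + 1/n₂)] − 2.576 ).

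With 30 and 30, √(1/30 + 1/30) = 0.258. Unadjusted: 0.67/0.258 = 2.595, and Φ(0.019) = 51%. With 12.8 and 22.6, √(1/12.8 + 1/22.6) = 0.350. Unadjusted: 0.67/0.350 = 1.915, and Φ(−0.66) = 25%.

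| Patients | Unadjusted | r = 0.3 | r = 0.5 | r = 0.7 |
|---|---|---|---|---|
| 30 vs 30 | 51% | 56% | 66% | 85% |
| 12.8 vs 22.6 (week 12) | 25% | 29% | 36% | 54% |

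The size depends on the assumed effect. At 0.5 SD with 30 per arm, power is 26% unadjusted and 29%, 37% and 55% adjusted. At 0.75 SD it is 63%, then 68%, 78% and 93%.

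**Step 4: repeated testing, only if it were done.** Four or five independent tests at 0.01 give 1 − 0.99⁴ = 3.9% or 1 − 0.99⁵ = 4.9%. Simulating normal test statistics with correlation 0.5 to 0.7 between visits gives 3.0-4.1%.

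**The case against.** Much can be said for the plan.

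- **Baseline is not ignored throughout.** Time to deterioration is defined from baseline and has its own method. It may be the measure meant for the 0.01 test. This stands, so the point concerns the scores only, and the plan should say which measure carries the alpha.
- **Repeated testing is not stated.** A reader might infer that the tests are run at every visit, or that the choice between t and Mann-Whitney will follow inspection of the data. Section 7 says neither. Step 4 is therefore conditional.
- **Blood cells.** A reader might extend the criticism to "Peripheral blood cells will be analyzed using Sidak's multiple comparison test". The documents do not support that. Sidak is a multiplicity adjustment that can follow a repeated-measures model or contrasts with baseline. Blood counts, T cell subsets and AFP are also marked at the out-of-group follow-up visit in the Section 6 table, so their collection is not confined to patients still progression-free. Section 4 does not list them as endpoints.
- **Attrition is easily overstated.** Counting only those progression-free at week 12 gives about 8 against 20. Those due a form number about 13 against 23. The imbalance remains, but is smaller.
- **A mixed model does not restore the randomised comparison by itself.** It uses patients' earlier scores, but depends on scores after progression being missing at random given what was observed. This stands, and the fix must say so.

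**Conclusion.** The point holds for QLQ-C30 scores, as a gap in specification and a readily available improvement. It does not show that the planned test would be invalid at a visit with complete data. The primary PFS analysis is unaffected.

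The direction of the precision gain is certain for any non-zero correlation. Its size is not, because the correlation and the 0.67 SD effect are assumptions. The figures also use a normal approximation. The gain applies at full enrolment and at the reduced week-12 numbers, but at week 12 power stays low even after adjustment, at 54% or less for correlations up to 0.7. Adjustment alone therefore does not rescue a late single-visit comparison.

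The unequal selection at later visits follows from the plan's own medians and its stopping of QoL collection at progression, under exponential PFS with no other losses. It would be smaller if the arms differed less in PFS. Whether the QoL error rate would exceed its 0.01 share cannot be settled from the documents.

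**What to change.** In Section 7, replace the t or Mann-Whitney test of QLQ-C30 scores with one mixed model for repeated measures. Include baseline score, arm, visit and arm-by-visit interaction, and fit it to all randomised patients with a post-baseline value. In the same paragraph:

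1. Name one QLQ-C30 scale and one contrast: the mean difference between arms over weeks 4, 8 and 12.
2. State whether that contrast or time to deterioration takes the 0.01 test, and label the other as supportive.
3. State that the model assumes scores are missing at random, and add a sensitivity analysis for scores missing after progression.

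The cost is SAP wording, a decision on the scale, and routine programming in the SAS software already planned. No additional data are needed.

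### Fisher's exact test at 0.01 with 30 per arm has a true size of at most 0.62%; an exact unconditional test for ORR and DCR would add about 1 to 12 points of power, depending on response rates the plan does not give

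*Combined protocol and SAP*

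**What the plan says.** Everything relevant is in Section 7 (Statistical Analysis) unless noted.

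- **Test.** Categorical variables "will be presented as the frequency and percentage, and will be compared using Fisher's exact tests". No other test is named for ORR or DCR, which Section 4 defines as proportions of patients, so this rule covers them by inference.
- **Level.** The overall 0.05 is divided equally "for tests of PFS, OS, ORR, DCR, and QoL according to the Bonferroni method", which gives each endpoint a two-sided 0.01.
- **Decision rule.** TAE-iNKT is declared better if PFS, and/or the secondary endpoints taken all together, "are statistically significant at a two-sided significance level of 0.01". ORR and DCR enter only through the second branch.
- **Sample size.** The bracketed text gives "allocation ratio of 1:1, n=30 patients in each group". The same sentence also says "the trial design was powered for 60 patients to be randomly assigned in each group", which read literally would mean 60 per arm. Drop-out of 20% is allowed for.
- **Power.** The only power statement is for PFS, "corresponding to a hazard ratio (HR) of 0.33 in terms of median PFS". No expected ORR or DCR appears for either arm, and no power is stated for them.
- **Denominator.** Section 4 counts patients with no tumour assessment after baseline as non-responders, so 30 per arm is the natural denominator.

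**The concern.** Fisher's test conditions on both margins of the 2 x 2 table. With 30 per arm, few p-values are attainable for a given margin, and the largest one below 0.01 is often well below it. The test then spends only part of the level it was given. This comes after the Bonferroni split has already cut that level from 0.05 to 0.01.

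Unconditional exact tests guarantee the same 0.01 over all values of the common response rate and leave less of it unused. What is at stake is power for two of the five endpoints that share the alpha, at no cost in patients. The choice has to be fixed in advance, because changing the test once results are known would not be credible.

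**Working it through.** **Inputs.** From Section 7: Fisher's test, two-sided p < 0.01, 30 per arm. Assumed: the response rates, taken as all pairs from 5% to 95% in steps of 5 points.

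**1. The plan's own figures.** The level is 0.05 / 5 = 0.01, as stated. The sample size can be checked with Freedman's formula, events = (z for alpha/2 + z for power)² x ((1 + HR)/(1 − HR))². With HR = 1/3 the second factor is 2² = 4.

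- At 0.01: (2.576 + 0.842)² x 4 = 46.7, so 47 events; 47 / 0.8 = 58.75, so 59, against 60 stated.
- At 0.05: (1.960 + 0.842)² x 4 = 31.4, so 32 events; 32 / 0.8 = 40.

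The plan does not name its formula, so this is only suggestive, but it supports reading 60 as the total (30 per arm) planned at 0.01. That the text says "The trial was designed to use a 2-sided 5% type I error and had 80% power" is a separate matter.

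**2. True size of Fisher's test.** There are 31 x 31 = 961 possible outcomes (x, y). Size at common rate p is the sum, over all tables with Fisher p < 0.01, of Bin(x; 30, p) x Bin(y; 30, p).

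| Common rate | 10% | 15% | 20% | 25% | 30% | 40% | 50% |
|---|---|---|---|---|---|---|---|
| True size | 0.08% | 0.21% | 0.29% | 0.35% | 0.39% | 0.53% | 0.62% |

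The maximum over rates from 0.001 to 0.999 is 0.622%, at 50%. Size is below 0.4% for rates under about 31% or over about 69%. So at least 1 − 0.622 = 38% of the allotted 0.01 goes unused.

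**3. An exact unconditional test.** Boschloo's test orders tables by the Fisher p-value and takes the largest cut-off whose maximum size stays at or below 0.01. At 30 per arm that cut-off is 0.0169, with maximum size 0.91%. No Fisher rejection is lost and 32 tables are added. Barnard's test with the pooled Z statistic gives the identical region.

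Example: 2 of 30 control responders against 11 of 30 treated gives Fisher p = 2 x [sum over k = 0 to 2 of C(30,k) C(30,13−k)] / C(60,13) = 0.0102. Fisher does not reject and needs 12; Boschloo rejects at 11. With 5 of 30 in the control arm, the thresholds are 16 and 15.

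**4. Power.** This is the same sum with Bin(x; 30, p1) x Bin(y; 30, p2). Gains are taken before rounding.

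| Assumed rates | Fisher | Unconditional | Gain (points) |
|---|---|---|---|
| 5% vs 30% | 34.6% | 46.5% | 11.9 |
| 10% vs 40% | 43.0% | 53.9% | 11.0 |
| 10% vs 50% | 74.2% | 82.1% | 8.0 |
| 20% vs 55% | 51.2% | 59.8% | 8.5 |
| 40% vs 75% | 50.7% | 55.8% | 5.1 |
| 20% vs 65% | 81.3% | 84.7% | 3.4 |
| 30% vs 60% | 34.6% | 37.8% | 3.2 |
| 30% vs 65% | 50.7% | 52.9% | 2.2 |
| 30% vs 70% | 66.9% | 68.5% | 1.6 |
| 25% vs 75% | 90.8% | 91.4% | 0.7 |

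Power is unchanged if each rate is replaced by 100% minus itself, so 50% vs 80% equals 20% vs 50% (35.0% to 44.3%). Over the 55 pairs where Fisher's power is 30% to 95%, the gain runs from 0.7 to 11.9 points, median 6.2. It is under 5 points in 38% of them.

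**5. Sensitivity to sample size.** With 30 x 0.8 = 24 per arm, Fisher's maximum size is 0.55% and the gain 1.2 to 11.9 points. With 60 per arm, the literal wording, the figures are 0.63% and 1.8 to 7.1 points.

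**The case against.** The strongest defence is that the plan contains no mistake here. Fisher's test is pre-specified, keeps its level, and does so conditionally on the margins as well as unconditionally; Boschloo's guarantee is unconditional only. Preferring one over the other is a long-standing choice of method. This stands. A reader might infer that Fisher's test gives power away for nothing, but the conditional guarantee is something, even if few would trade several points of power for it.

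A reader might also infer a general loss of 5 to 12 points. The documents do not support that, because they give no expected ORR or DCR. The range fits low control rates, which is plausible for ORR after TACE failure but is an assumption, and the mirror case of high rates. It fails for mid-range pairs, which could apply to DCR because that endpoint also counts stable disease.

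The consequence is also limited. ORR and DCR are secondary, the sample size rests on PFS, and PFS alone can satisfy the decision rule. The branch that uses ORR and DCR also needs OS and QoL to reach 0.01, and nothing here shows how far the chance of meeting it would change. In several scenarios power stays near 40% to 60% under either test: 30 per arm and the five-way split are the main limits.

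One possible objection carries no weight at the planned size, namely that Boschloo's and Barnard's tests might disagree. At 30 per arm their rejection regions are the same.

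**Conclusion.** The point holds as a cheap efficiency improvement. At 30 per arm and a two-sided 0.01, an exact unconditional test has the same guaranteed level, loses no Fisher rejection, and has higher power at every pair examined: 0.7 to 11.9 points, median 6.2. The size figures (0.62% and 0.91%) depend only on the arm size and the level. The power gains also depend on assumed rates, so no single figure should be quoted as the loss in this trial. The result assumes that ORR and DCR fall under the categorical-variable rule and are analysed with 30 per arm; it keeps its direction at 24 and 60. It does not make Fisher's test invalid, and it does not make the trial adequately powered for ORR or DCR.

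**What to change.** In Section 7, for ORR and DCR only, name one exact unconditional test at two-sided 0.01: Boschloo's, or Barnard's with the pooled Z statistic. Report the difference in proportions with an exact unconditional confidence interval. Name a single test and its ordering statistic, because the two regions need not coincide if the arms are not 30 and 30. Keep Fisher's test for baseline and adverse-event tables.

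Do not substitute an uncorrected chi-square test, whose true size reaches 1.35% at 30 per arm. A mid-p version of Fisher's test recovers only part of the loss.

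The cost is one sentence and a check that the planned SAS 9.4 set-up can run the chosen test and interval. No extra patients are needed. The downsides are small: error control is no longer conditional on the margins, and the test is less familiar to readers.
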